5.6.6. PSSD Assessments

The Psoriasis Symptom and Sign Diary (PSSD) is a patient-reported outcome (PRO) questionnaire designed to measure the severity of psoriasis symptoms and signs for the assessment of treatment benefit. The PSSD includes 11 items covering symptoms (itch, pain, stinging, burning and skin tightness) and subject observable signs (skin dryness, cracking, scaling, shedding or flaking, redness and bleeding) using 0 (=absent) to 10 (=worst imaginable) numerical rating scales for severity. Two subscores will be derived: the psoriasis symptom score and the psoriasis sign score. A higher score indicates more severe disease. Additionally, the single items itch, pain, and scaling and also the other single items will be evaluated. The subjects will complete the 7-day recall version of the PSSD as indicated in the Time and Events Schedule.

The calculations of PSSD symptom, and sign scores are listed below.

Symptom Score (0-100)

- a) Symptom score includes itch (Q1), pain (Q11), stinging (Q10), burning (Q9) and skin tightness (Q4).
- b) Averaging items on the symptom scores when at least 3 items ($\geq 50\%$ of 5 items) on this scale are answered. Then, the average value is converted into 0-100 scoring such that Symptom score = average value x 10 with 0 representing the least severe and 100 the most severe. Otherwise, the symptom score will be set to missing.

Sign Score (0-100)

- a) Sign score includes skin dryness (Q2), cracking (Q3), scaling (Q5), shedding or flaking (Q6), redness (Q7) and bleeding (Q8).
- b) Averaging items on the sign scores when at least 3 items ($\geq 50\%$ of 6 items) on this scale are answered. Then, the average value is converted into 0-100 scoring such that Sign score = average value x 10 with 0 representing the least severe and 100 the most severe. Otherwise, the sign score will be set to missing.

The following endpoints will be evaluated:

- PSSD Signs and Symptoms aggregate scores over time

For analysis groups III to V (and overall) only, the PSSD Signs and Symptom scores at scheduled study visits and changes from baseline (R0 visit) will be tabulated by descriptive statistics (OC analysis). No inferential statistics will be provided.

Update before start of programming for the final week 220 analysis: Values by scheduled study visit and changes from baseline (R0 visit) will also be tabulated by descriptive statistics (OC analysis) for the PSSD items 1, 9, 10 and 11, for all subjects and the analysis groups (no further subgroups).

- Change from baseline (R0 visit) in PSSD Signs and Symptoms scores 24 weeks after start of re-treatment

The change from baseline (R0 visit) to week R24 will be tabulated for all subjects of analysis groups III to V (total only). A univariate ANCOVA model will be used to test the difference between subgroups by disease duration; the change from baseline being the dependent variable, and disease duration and baseline as independent variables. A 95% confidence interval for the difference in LS means and nominal p-value will be calculated based on contrast test statistics. The LS means, the LS mean difference and the standardized mean difference (computed according to Hedges' g), together with the 95% CI and two-sided nominal p-value, will be provided from the ANCOVA model.

5.7. Safety Analyses

All safety analyses for the Re-treatment phase will be based on the Safety analysis set. Data from the safety follow-up at week R28 will be included in the analyses. Safety data, including but not limited to, adverse events (AEs), serious AEs, infections, serious infections, changes in laboratory assessments, and changes in vital signs, will be evaluated. Treatment-emergent AEs (TEAEs) will be summarized by Medical Dictionary for Regulatory Activities (MedDRA) system organ class (SOC) and Preferred Terms (PT).

For all continuous safety variables, descriptive statistics will include the N, mean, standard deviation, median, quartiles, minimum, and maximum. Categorical variables will be summarized using frequency counts and percentages. All tables will provide results by analysis group and overall.

5.7.1. Extent of Exposure

The number and percentage of subjects who received study agent during the Re-treatment phase will be summarized by visit. Descriptive statistics will be presented for the number of study agent administrations.

5.7.2. Adverse Events

The verbatim terms used in the eCRF by investigators to describe adverse events will be coded using the Medical Dictionary for Regulatory Activities (MedDRA). Any AE occurring at or after the day of first re-treatment dose is considered to be treatment-emergent. If the onset date is recorded partially only or is completely missing, then the event is regarded as treatment-emergent unless it is known to be prior to the first dose of re-treatment based on partial onset date or

resolution date. All reported treatment-emergent adverse events (TEAEs) will be included in the detailed analysis.

For each adverse event (ie, Preferred Term) the number and percentage of subjects who experience at least one occurrence of the given event will be provided. Summary tabulation will also provide the number of events, if applicable.

Summary tables will be generated for:

- AEs
- TEAEs
- TEAEs by severity
- TEAEs by relationship to study agent
- TEAEs leading to discontinuation of study agent
- Infections
- Injection site reactions
- Serious TEAEs (TESAEs)
- Serious infections
- Serious injection site reactions.

In addition to the summary tables, listings will be provided for subjects who:

- Had (S)AEs
- Had AEs leading to discontinuation of study agent.

Deaths will be displayed by analysis group. Frequencies for the following parameters will be included in the summary table:

- Number of subjects who died
- Cause of death
- Relationship to study agent (yes/no) (yes includes the following eCRF items: possible, probable, very likely).

A listing of subjects who died will also be provided.

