11.7. Safety Analyses

Safety data, including but not limited to, AEs, SAEs, infections, serious infections, changes in laboratory assessments, and changes in vital signs will be summarized. Treatment-emergent AEs (TEAEs) will be summarized by treatment group and Medical Dictionary for Regulatory Activities (MedDRA) system organ class (SOC) and preferred terms (PT).

Analysis Data Set

The safety analyses will be performed separately for each Study Part. For all safety analyses, all subjects treated with at least one dose of study drug will be included. For all the safety analyses, subjects will be analyzed according to the treatment they actually received.

Adverse Events

The verbatim terms used in the eCRF by investigators to identify AEs will be coded using MedDRA. All reported AEs with onset during the treatment phase (ie, treatment-emergent AEs, and AEs that have worsened since baseline) will be included in the analysis. For each adverse event, the percentage of subjects who experience at least 1 occurrence of the given event will be summarized by treatment group.

Summaries, listings, datasets, or subject narratives may be provided, as appropriate, for those subjects who die, who discontinue treatment due to an adverse event, or who experience a severe or a serious AE.

The following analyses will be used to assess the safety of subjects in the study:

- The incidence and type of AEs.
- The incidence and type of SAEs.
- The incidence and type of infections.
- The incidence and type of reasonably related AEs.
- The incidence and type of injection site reactions.
- The laboratory parameters and change from baseline in laboratory parameters (hematology and chemistry).

Clinical Laboratory Tests

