12.1. Definitions

12.1.1. Adverse Event Definitions and Classifications

Adverse Event

An adverse event (AE) is any untoward medical occurrence in a clinical study subject administered a medicinal (investigational or non-investigational-) product. An AE does not necessarily have a causal relationship with the treatment. An AE can therefore be any unfavorable and unintended sign (including an abnormal finding), symptom, or disease temporally associated with the use of a medicinal (investigational or non-investigational) product, whether or not related to that medicinal (investigational or non-investigational) product. (Definition per International Council for Harmonization- [ICH]).

This includes any occurrence that is new in onset or aggravated in severity or frequency from the baseline condition, or abnormal results of diagnostic procedures, including laboratory test abnormalities.

Note: The Sponsor collects AEs starting with the signing of the ICF (refer to Section 12.3.1 for time of last AE recording).

Serious Adverse Event

A serious AE (SAE) based on ICH and EU Guidelines on Pharmacovigilance for Medicinal Products for Human Use is any untoward medical occurrence that at any dose:

- Results in death
- Is life-threatening
(The subject was at risk of death at the time of the event. It does not refer to an event that hypothetically might have caused death if it were more severe.)
- Requires inpatient hospitalization or prolongation of existing hospitalization
- Results in persistent or significant disability/incapacity
- Is a congenital anomaly/birth defect
- Is a suspected transmission of any infectious agent via a medicinal product
- Is medically important*

*Medical and scientific judgment should be exercised in deciding whether expedited reporting is also appropriate in other situations, such as important medical events that may not be immediately life threatening or result in death or hospitalization but may jeopardize the subject or may require intervention to prevent any of the other SAE outcomes listed above. These should usually be considered serious.

If a serious and unexpected AE occurs for which there is evidence suggesting a causal relationship between the study drug and the event (eg, death from anaphylaxis), the event must be reported as a serious and unexpected suspected adverse reaction even if it is a component of the study endpoint (eg, all-cause mortality).

Unlisted (Unexpected) Adverse Event/Reference Safety Information

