5.1. General Considerations

The following general analysis definitions refer only to the Re-treatment phase.

The statistical analysis of the Re-treatment phase will be exploratory. Inferential statistics (ie, confidence intervals) will be provided only for the visit R24 data of endpoints in the Re-treatment phase. With the exception of the secondary endpoint (PASI <3 at visit R24), all other summary tables will be purely descriptive (for comparison of subgroups see below).

Descriptive statistics will include counts and proportions for categorical data, and mean, SD, median, interquartile range, and range, for continuous data. Graphical data displays will also be used to summarize the data.

Time-to-event endpoints will be analyzed using the Kaplan-Meier product limit method to estimate the survival distributions and the median time-to-event.

For selected endpoints, subgroups will be analyzed to evaluate – among others – the effect of randomization to treatment frequency (performed for Study Part 2) and the effect of disease duration (assessed in Study Part 1 as stratification factor) on efficacy endpoints assessed after re-treatment was started; subgroups are defined in Section 5.8.8. Subgroups will exploratorily be compared using the two-sided unadjusted two-group Chi² test acc. to Wald (binary endpoints), the log-rank test (time-to-event endpoints) or a univariate analysis of covariance (ANCOVA) model with fixed effect for subgroup and baseline value as covariate (continuous endpoints).

Individual subject data listings will be presented parameter-wise and will be sorted by study site, subject's identification number and study visit, if applicable (without a preceding classification variable).

Note: Statistical analysis for safety of the Re-treatment phase will not include analyses of study data recorded before start of re-treatment, as safety for Study Parts 2 and 3 was already evaluated in previous analyses. However, the analysis for efficacy of the Re-treatment phase will include the preceding study visits before R0 (the start of the Re-treatment phase). For each subject, up to five pre-R0 visits will be selected based on the 12-week visit schedule, where visit R-1 is the regular visit before the R0 visit. Data of Study Parts 1, 2 and 3 will be included in the individual subject data listings.

A more detailed description of the planned statistical analyses is provided in the sections below.

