6.2. Appendix 2 Changes to Protocol-Planned Analyses

No important changes from the planned analyses specified in the protocol and its amendments were applied.

However, the time point of analyses is changed slightly. While the CSP states that “interim analyses are planned after all subjects have completed their visit at week 116 (or at week 144 in case of subjects entering the re-treatment arm in week 116) and at week 164 (or at week 192 in case of subjects entering re-treatment arm in week 164). The final analysis will be performed after all subjects have completed their visit at week 220 (or at week 248 in case of subjects entering the re-treatment arm in week 220)”, it was decided to split the analyses of group 3a/3b subjects and the analyses of group 3c subjects (Re-treatment phase). By this, the results for the week 116/164/220 analyses of study groups 3a and 3b will be available as soon as possible. A separate SAP is written for the analysis of the analysis of Study Part 3 data obtained before re-treatment starts.

In addition, some new analyses have been added to the evaluation; see section 5.6 for details.

The initial SAP, prepared before the Dry-run meeting for the first interim analysis (re-treatment started until week 116), was updated several times during the course of the study:

- Changes introduced before the Week 116 re-treatment analysis:
 - The analysis window for week R8 was enlarged from Day 20 to Day 85 and for week R16 from Day 86 to Day 127.
 - The Kaplan-Meier analysis for the time to regain disease control is not performed on observed cases but as NRI analysis.
 - DLQI values by study visit are also displayed for selected subgroups according to Section 5.8.8.
 - Subgroups C and G are not evaluated.
 - DLQI values over time are displayed for subgroups B, D, and H.
 - Subgroup I is added.
 - Demographic data are displayed separately for each subgroup.
- Changes introduced before the Week 220 re-treatment analysis:
 - Single items of DLQI and PSSD are added for analysis.
 - The subgroups by time of entering the Re-treatment phase are re-defined.
 - New subgroups J, K, L and M are added to the analysis.
 - The Kaplan-Meier analysis for the time to regain disease control is regarded as OC analysis while PASI values under prohibited medication are not used for analysis.

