5.4.1. Adverse Events

The verbatim terms used in the eCRF by investigators to describe adverse events (AEs) are coded using the Medical Dictionary for Regulatory Activities (MedDRA). For analysis, AEs will be summarized by MedDRA system organ class (SOC) and Preferred Terms (PT) for each analysis group and overall.

For each analysis set, a separate time period will be considered for analysis:

Analysis set	Time period to be analyzed	Excluded time period
All subjects treated in Study Part 1 (N = 880)	Date of first dose (week 0) until study end	Date of week 28 dose and thereafter
All subjects treated in Study Part 2 (N = 822) #	Date of first verum dose (week 28 or week 36) until Date of last verum dose (week 52 or week 60) in Study Part 2 plus 90 days	Date of re-treatment and thereafter
All subjects randomized for Study Part 2 (N = 297) §	Date of randomization (week 28) until Date of last verum dose (week 52 or week 60) in Study Part 2 plus 90 days	Date of re-treatment and thereafter
All subjects with a Withdrawal phase longer than 90 days (N < 273)	91 st day after last verum dose in Study Part 2 until the day before re-	Date of re-treatment and thereafter

Analysis set	Time period to be analyzed	Excluded time period
	treatment is started (or study end if no re-treatment was started)	
All subjects who started re-treatment (N = 236)	Date of first re-treatment dose (week R0) until study end	None

In this analysis, subjects will be evaluated as well by analysis groups (super responders and non-super-responders).

§ In this analysis, subjects will be evaluated only by analysis groups (treated q8w and treated q16w).

If the AE onset date is recorded partially only or is completely missing, then the event will be considered for analysis unless it is known to be prior to the respective time period based on partial onset date or resolution date. Rules to impute a partial or missing onset date are presented in Section 5.1.5. In case a subject missed the week 68 visit, the date of the week 68 visit will be estimated as 8 weeks (56 days) after the week 60 visit.

For each AE, the number and percentage of subjects who experience at least one occurrence of the given event (SOC, PT) will be summarized by analysis group and overall. Summary tabulation will also provide the number of events, if applicable.

Summary tables will be provided – separately for each analysis set – for:

- AEs
- AEs by highest relationship to study agent
- AEs by worst severity
- Infections

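### Re-treatment SAP 5.7.2 defines treatment-emergent by onset alone, omits the worsened events that protocol 11.7 includes, and does not list this as a change

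*SAP*

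**What the plan says.** Protocol 11.7 sets the rule for adverse events: "All reported AEs with onset during the treatment phase (ie, treatment-emergent AEs, and AEs that have worsened since baseline) will be included in the analysis". Protocol 12.1.1, defining an adverse event, adds: "This includes any occurrence that is new in onset or aggravated in severity or frequency from the baseline condition".

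Re-treatment SAP 5.7.2 uses a shorter rule: "Any AE occurring at or after the day of first re-treatment dose is considered to be treatment-emergent". For partial or missing dates, "the event is regarded as treatment-emergent unless it is known to be prior to the first dose of re-treatment based on partial onset date" or on resolution date. Section 5.1 of the same SAP adds: "Statistical analysis for safety of the Re-treatment phase will not include analyses of study data recorded before start of re-treatment". Appendix 2 (6.2) states: "No important changes from the planned analyses specified in the protocol and its amendments were applied". It then itemises several smaller changes, including the wider R8 visit window, but not this one.

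The overall safety SAP (section 4 and 5.4.1) gives each analysis set its own time period. It too tests partial or missing onset dates against the start of that period and has no provision for worsening. Its list of tables includes "AEs by worst severity", without saying whether the grade must have been reached within the period.

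**The concern.** Protocol 11.7 names worsened events as part of what is analysed. The re-treatment SAP keeps the onset part and is silent on worsening. Within that SAP, R0 is the baseline for the phase (5.1.4), and laboratory values and vital signs are assessed by change from R0 (5.7.3). Worsening is thus captured for those measures but not for adverse events.

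Most re-treated subjects came from a withdrawal phase, so events still ongoing at the first re-treatment dose are plausible. If such an event becomes severe or serious after re-dosing and the site updates the existing record, the tables meant to describe safety on re-treatment do not show it. The overall safety SAP was written to describe treatment, withdrawal and re-treatment across the whole study. There the same event stays in the earlier period, and its worst grade may be shown there although it was reached later.

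**Working it through.** This is a classification rule, so the check sets the rules side by side and runs one constructed case through them.

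**Set sizes (overall safety SAP 4.5).** Re-treated after withdrawal 227, re-treated without withdrawal 3 + 6 = 9, total 227 + 9 = 236, as stated. Share with a withdrawal phase: 227/236 = 96.2%.

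**Constructed case.** Onset week 100, first re-treatment dose week 104, worsening week 108.

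| Rule | Counted under re-treatment? |
|---|---|
| Re-treatment SAP 5.7.2, one record (100 is before 104) | No |
| Protocol 11.7, onset or worsening (108 is after 104) | Yes |
| Re-treatment SAP 5.7.2, new record opened at week 108 | Yes |

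The SAP and the protocol therefore differ only when worsening is kept in the original record.

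**Where the single record goes in the overall safety SAP.** The withdrawal set (4.4) opens on day 91 after the last active dose in Part 2, and 91/7 = 13 weeks.

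- q8w: 60 + 13 = week 73.
- q16w: 52 + 13 = week 65.

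In the constructed case, onset at week 100 falls in the withdrawal set. An event starting in Part 2 but before week 73 (q8w) or week 65 (q16w) falls in the Part 2 set. The 9 subjects without a withdrawal phase have no drug-free period, so their earlier events cannot be placed in one.

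**Size.** The documents give no count of events ongoing at the first re-treatment dose that later worsened. As an assumption only, for the share of the 236 with such an event in a single record:

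- 0%: 0 subjects
- 1%: 0.01 × 236 = 2.4
- 2%: 0.02 × 236 = 4.7
- 5%: 0.05 × 236 = 11.8

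**The case against.** The strongest reply is that nothing is lost. Protocol 12.1.1 treats an aggravated condition as an adverse event, and the SAP's baseline for this phase is R0. Worsening after R0 could then be an event in its own right with its own onset date. The parenthesis in protocol 11.7 explains onset during the treatment phase, which fits that reading. If sites opened a new record for each worsening, the SAP rule captures it. This stands as a possibility, but neither the protocol nor the SAPs say that an ongoing event gets a new record when it worsens. On either reading the protocol includes worsened events, and the SAP wording does not secure that.

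There are partial safeguards. Re-treatment SAP 5.7.2 also has a general AE table, and its listings and death table are not labelled treatment-emergent. The general table is undefined, however, and the severity, relationship, discontinuation and serious-event tables are TEAE tables.

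A reader might infer more than the documents support:

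- **That the SAPs expressly exclude worsened events.** They are silent on them.
- **That the displaced harm always lands in the drug-free period.** It can fall in the Part 2 set, and 9 of the 236 subjects have no drug-free period.
- **That the tables are biased in favour of the drug.** The same onset rule keeps an event that starts on drug and worsens off drug in the on-drug sets, which works the other way. The net direction is not shown.
- **That the worst-severity table necessarily shows a later grade.** It could mean the worst grade among events within the period; the text does not settle it.
- **That the overall safety SAP breaches protocol 11.7.** That analysis was not planned in the protocol and is purely descriptive. The direct conflict is with the re-treatment SAP only.

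**Conclusion.** The point holds in a limited form. Re-treatment SAP 5.7.2 is narrower than protocol 11.7 and Appendix 2 does not declare it. For an event held in one record that begins before the first re-treatment dose and worsens or becomes serious afterwards, the re-treatment TEAE, severity and serious-TEAE tables are incomplete. In the overall safety SAP the same event is counted only in its period of onset, with the period limit on worst severity left unstated.

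The size is unknown. It is zero if worsening was always entered as a new record, and about 2 to 12 of the 236 subjects if 1% to 5% had a single-record event of this kind; that range is an assumption with no anchor in the documents. The confirmatory efficacy analysis is not touched. The change should be made because it restores the protocol's own rule at little cost.

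**What to change.** - **Re-treatment SAP 5.7.2.** Define treatment-emergent as onset at or after the first re-treatment dose, or earlier onset with an increase in severity or seriousness at or after that dose, in line with protocol 11.7.
- **Overall safety SAP 5.4.1.** Count a worsened event also in the period in which it worsened. Where the eCRF holds dated changes or separate records, limit worst severity to the grade reached in the period.
- **Both SAPs.** State how the eCRF records worsening of an ongoing event. If every worsening is a new record, that statement resolves the point.
- **Appendix 2 of the re-treatment SAP.** If worsened events cannot be identified from the data collected, list the departure from protocol 11.7.

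The cost is a sentence or two in each SAP and a rerun of the adverse event tables. Counts on re-treatment may rise slightly. The period-specific severity table is feasible only where dated severity changes or separate records exist, which the documents do not confirm.
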